4.1. Primary End Points + Time Points

To measure the effectiveness of sargramostim on restoring lung homeostasis, the **primary endpoint** of this intervention is **measuring oxygenation** after 5 DAYS of inhaled (and intravenous) treatment through assessment of pretreatment (day 0) and post-treatment (day 5) ratio of PaO₂/FiO₂ and through measurement of the P(A-a)O₂ gradient, which can easily be performed in the setting of clinical observation of patients admitted to the COVID -19 ward or ICU COVID-19 unit. Preferentially, this measurement should be done in the upright position, while breathing room air for a minimum of 3 minutes. If this is impossible due to need for supplemental oxygen, FiO₂ and oxygen supplementation method should be recorded in patient record, so that A-a gradient can be normalized for age expected normal A-a gradient while on supplemental oxygen use.

During the 5 day treatment period, we will perform daily measurements of oxygen saturation (pulse oximetry) in relation to FiO₂, and the slope of alterations in this parameters could also be an indicator that our hypothesis is correct.

If the patient leaves hospital prior to the day 6 analysis point, oxygenation at day of discharge will be used as value for measuring primary endpoint.

Improvement will be expressed as % of patients showing an improvement in $P(A-a)O_2$ gradient and PaO_2/FiO_2 ratio between day 6 and day 1 of at least 25%; at least 33% and at least 50% in each treatment arm and expressed also as mean and median change in $P(A-a)O_2$ gradient and PaO_2/FiO_2 ratio comparing D6 to D1 in both treatment arms.

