9.1. Randomization

In this open label trial patients will be randomized in a 1:1 ratio. Randomization in Belgium will be done using REDCap (electronic IVRS system).

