9.2. Study specific interventions

This is a hospital based intervention trial, in which patients with COVID-19 will be treated at least for 5 days with sargramostim. Patients with COVID-19 infection and respiratory failure are severely ill, and will require multiple daily clinical exams, blood sampling, vital parameter measurements, blood oxygenation measurements, and chest X-rays. These are all part of the clinical management plan of the patients, and data stored in the electronic patient file will be used as part of the assessment of efficacy and safety profile of sargramostim.

On screening, blood sample will be taken, preferentially during routine blood sampling, to determine exclusion criteria (pregnancy, high ferritin level).

On day 1, prior to sargramostim treatment in group A, and during the day in group B control patients, a tube of blood serum (5 ml) and an EDTA tube (10 ml) will be collected for measuring blood cytokine and chemokine levels, and activation of immune cells in selected centers. Also in each center, an arterial blood gas determination via arterial puncture will be taken. This sample should be taken in an upright position, while breathing room air for a minimum of 3 minutes. If this is impossible due to dependency on supplemental oxygen, FiO₂, oxygen flow rate, and method of oxygen delivery should be noted in the patient file. If arterial blood gas is taken within 24h before first dose administration, the arterial blood gas of screening can be used as D1 value.

Method	O ₂ flow (l/min)	Estimated FIO ₂ (%)
Nasal	≤ 1,5	24
	> 1,5 and ≤ 2,5	28
	> 2,5 and ≤ 3,5	32
	> 3,5 and ≤ 4,5	36
	> 4,5 and ≤ 5,5	40
	> 5,5 and ≤ 15	44
Nasal pharyngeal cannula	≤ 0,5	24
	> 0,5 and ≤ 1	28
	> 1 and ≤ 1,5	30
	> 1,5 and ≤ 2,5	32
	> 2,5 and ≤ 3,5	36
	> 3,5 and ≤ 4,5	40
	> 4,5 and ≤ 5,5	50
Face mask	> 5,5 and ≤ 6	60
	≤ 1,5	24
	> 1,5 and ≤ 2	28
	> 2 and ≤ 2,5	30
	> 2,5 and ≤ 3,5	32
	> 3,5 and ≤ 4	36
	> 4 and ≤ 4,5	38
	> 4,5 and ≤ 5,5	40
Face mask with reservoir	> 5,5 and ≤ 7	50
	> 7	60
	≤ 2,5	28
	> 2,5 and ≤ 3,5	32
	> 3,5 and ≤ 4,5	40
	> 4,5 and ≤ 5,5	50
	> 5,5 and ≤ 6,5	60
	> 6,5 and ≤ 7,5	70
	> 7,5 and ≤ 8,5	80
	> 8,5 and ≤ 9,5	90
	> 9,5	95

On day 6 or on day of discharge before day 6 , a tube of blood serum (5ml) and an EDTA tube (10 ml) will be collected for measuring blood cytokine and chemokine levels, and activation of immune cells in selected centers. Also in each center, an arterial blood gas determination via arterial puncture will be taken.

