12.1. Sample size calculation

The outcome(s) on which the sample size calculation is based upon, is the primary endpoint measurement of oxygenation, defined as ratio of $\text{PaO}_2/\text{FiO}_2$ and P(A-a)O_2 .

Sample calculation and power analysis have been performed using Genstat. The target difference is the difference measured at the primary endpoint (at day 6) between the control and the treated group. Given a sample size of 40 patients each, a minimal improvement of 10% in the treated group relative to the control group will be detected as significant at a significance level of 0,01 with a power of 0.90. The error variance was set at 100 units, corresponding with a standard deviation of 10 units.

The post-treatment evaluations should be assessed within 24 hours of the last dose of treatment. That is, Day 6 will be the timepoint for measures of efficacy endpoints based on 5 days of treatment, and Day 10 for patients who complete 10 days of treatment. If the patient is discharged from hospital prior to the day 6 (or day 10) efficacy evaluations, the values at day of discharge will be used as value for measuring efficacy endpoints.

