12.2. Type of statistical methods

All endpoints will be summarized and where relevant represented graphically

A detailed statistical analysis plan (SAP) has been set up by EffectStats LLC, Cambridge Massachusetts, USA. The statistical tests to be used to look at improvements in oxygenation between treatment groups will be a Chi-square test. Mortality frequencies will be analyzed using Wald test.

Key timepoints of interest for endpoints include Day 6 and Day 11, where data are available. All available efficacy data will be tabulated and presented for all patients in the mITT Population.

Oxygenation after 5 days of Sargramostim Intervention

To measure the effectiveness of sargramostim on restoring lung homeostasis, the primary endpoint of this intervention is measuring oxygenation after 5 days of inhaled (and intravenous) treatment through assessment of pretreatment and post-treatment ratio of $\text{PaO}_2/\text{FiO}_2$, $\text{SpO}_2/\text{FiO}_2$ and through measurement of the P(A-a)O_2 gradient. During the 5 day treatment period, daily measurements of oxygen saturation (pulse oximetry) in relation to FiO_2 will be performed. Negative value of P(A-a)O_2 gradient would be removed from the primary analysis.

P(A-a)O_2 gradient, $\text{PaO}_2/\text{FiO}_2$ ratio and $\text{SpO}_2/\text{FiO}_2$ are defined as:

$\text{P(A-a)O}_2 \text{ gradient} = [(\text{FiO}_2) \times (\text{Atmospheric Pressure} - \text{H}_2\text{O Pressure}) - (\text{PaCO}_2/0.8)] - \text{PaO}_2$

$\text{PaO}_2/\text{FiO}_2 = \text{Partial Pressure Oxygen/Fraction of Inspired Oxygen} \times 100$

$\text{SpO}_2/\text{FiO}_2 = \text{Oxygen Saturation/ Fraction of Inspired Oxygen} \times 100$

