Comparison will be between active group A receiving sargramostim on top of standard of care and control group B receiving standard of care. The change from baseline and daily change from baseline in oxygenation/respiratory parameter of P(A-a)O_2 gradient, ratio of $\text{PaO}_2/\text{FiO}_2$ and ratio of $\text{SpO}_2/\text{FiO}_2$ will be evaluated and summarized between group A and group B at Day 6. The difference of change from baseline between two groups will be tested by a t-test. In general, the last observed measurement prior to the first dose of study treatment occurred on Day 1 visit will be considered the baseline measurement. Day 6 is the primary analysis point. If the patient leaves hospital prior to the day 6 analysis point, oxygenation at day of discharge will be used as value for measuring primary endpoint.

The analyses described above will also be performed between group A (early 5 day intervention with sargramostim) and group D (late 5 day intervention with sargramostim). Change from baseline (D1) to Day 10, daily change from baseline (D1) at Day 10 in oxygenation/respiratory parameter of P(A-a)O_2

gradient, ratio of $\text{PaO}_2/\text{FiO}_2$ and ratio of $\text{SpO}_2/\text{FiO}_2$ will be summarized as well. A t-test will be conducted to compare the difference between the groups.

The same analyses will be repeated for pathological oxygenation parameter of P(A-a)O_2 gradient, ratio of $\text{PaO}_2/\text{FiO}_2$ and ratio of $\text{SpO}_2/\text{FiO}_2$ including summary of their value and change from baseline at Day 6 and Day 10. A waterfall plot will be used to represent the change from baseline and percentage change from baseline on Day 6 for 1) oxygenation parameter of P(A-a)O_2 gradient; 2) pathological oxygenation parameter of P(A-a)O_2 gradient; 3) ratio of $\text{PaO}_2/\text{FiO}_2$; 4) ratio of $\text{SpO}_2/\text{FiO}_2$. Percentage change from baseline of P(A-a)O_2 gradient and ratio of $\text{PaO}_2/\text{FiO}_2$ on Day 6 and follow-up will be summarized.

Reasons of missing AA gradient values on Day 6 will also be summarized.

The normal value of AA gradient for room air is calculated as: $2.5 + (0.21 \times \text{Age})$. All the results including change from baseline, and maximum change from baseline after 5 day intervention with sargramostim, normal AA gradient value for room air and flag of abnormality on Day 6 will be listed.

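### Section 12.2 names two different tests for the primary Day 6 oxygenation comparison, the list of primary measures varies between sections, and no measure or test is made the deciding one.

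*Protocol*

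**What the plan says.** **Tests.** Section 12.2 (Type of statistical methods) opens with "The statistical tests to be used to look at improvements in oxygenation between treatment groups will be a Chi-square test". Further on, for the comparison of groups A and B at Day 6 on the gradient, PaO2/FiO2 and SpO2/FiO2, it says "The difference of change from baseline between two groups will be tested by a t-test". No covariate is named.

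**Measures.** Sections 3.1, 4.1, 5.1 and 12.1 give the primary endpoint as PaO2/FiO2 and the P(A-a)O2 gradient. Section 12.2 restates it with SpO2/FiO2 as a third measure.

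**Expression of the result.** Section 4.1 contains the sentence that begins "Improvement will be expressed as % of patients showing an improvement in". It covers two measures, the gradient and PaO2/FiO2, with thresholds of 25%, 33% and 50%, and also asks for mean and median change. Section 12.2 lists the same cut-offs for the gradient and the pathological gradient, not for PaO2/FiO2, and says only that they will be summarised.

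**Sizing.** Section 12.1 rests on one between-group difference at Day 6. Its premise is "Given a sample size of 40 patients each, a minimal improvement of 10% in the treated group relative to the control group". With an SD of 10 units, the section claims that a difference of this size "will be detected as significant at a significance level of 0,01 with a power of 0.90". It does not say whether the test is one- or two-sided.

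**Baseline.** Section 12.2: "the last observed measurement prior to the first dose of study treatment occurred on Day 1 visit will be considered the baseline measurement". Section 9.2 takes the Day 1 sample "prior to sargramostim treatment in group A, and during the day in group B control patients".

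**The concern.** Section 12.2 attaches both a test of proportions and a test of means to the same endpoint and time point, on two or three measures, without ranking them. If PaO2/FiO2 passed the t-test and the gradient failed the chi-square test, or the reverse, the protocol would not say whether the trial had met its primary objective. In an open-label trial of 80 patients, leaving that choice open weakens any positive claim.

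Two further costs follow. The trial was sized on a difference in means, so a decision by chi-square would have less power than planned. And a Day 1 value is scheduled for every patient, but neither test uses it in the way that generally gives the most precise comparison.

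**Working it through.** **1. The plan's own figure.** Inputs from sections 9.1 and 12.1: 40 per arm, 1:1, SD 10, level 0.01, power 0.90. If 10% is read as 10 units, the standardised difference is d = 10/10 = 1.0, and the t-test has power 0.964 two-sided (0.981 one-sided), not 0.90. With 40 per arm, 90% power at two-sided 0.01 corresponds to 8.8 units, d = 0.881. The gap arises because no control mean is given to convert 10% into units. That is a separate matter; d = 0.881 is used below only as the effect for which the t-test has 90% power.

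**2. False positives at the stated 0.01.** Section 12.2 makes three t-tests explicit. Six chi-square tests (2 measures x 3 cut-offs) appear only if its opening sentence is joined to section 4.1. If all tests were independent:
- three tests: 1 - 0.99^3 = 0.030
- nine tests: 1 - 0.99^9 = 0.087

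The measures are correlated, so null trials were simulated (6,000 per setting, 40 per arm; between-measure correlation assumed, baseline to Day 6 correlation 0.5 assumed):

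| Between-measure correlation | Three t-tests | All nine |
|---|---|---|
| 0.5 | 0.028 | 0.064 |
| 0.7 | 0.023 | 0.054 |
| 0.9 | 0.021 | 0.052 |

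Repeats over correlations of 0.6 to 0.9 give about 2-3% for the three t-tests and 4-7% for all nine.

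**3. Power if chi-square decided.** Take a normal outcome with d = 0.881 and a cut-off giving control response p. The treated response is then q = 1 - Φ(z(1-p) - 0.881). Exact binomial power of the chi-square test at 0.01 with 40 per arm (p assumed):

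| p | q | Power |
|---|---|---|
| 0.2 | 0.516 | 0.66 |
| 0.3 | 0.639 | 0.69 |
| 0.4 | 0.735 | 0.68 |
| 0.5 | 0.811 | 0.66 |

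The same effect has 0.90 by t-test. A normal approximation at d = 0.863 gives slightly less, 0.62-0.67.

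**4. Change score against ANCOVA.** Let rho be the correlation between Day 1 and Day 6 and k the Day 1 SD divided by the Day 6 SD; the protocol gives neither. In units of the Day 6 variance:
- Var(change) = 1 + k² - 2k·rho
- Var(ANCOVA) = 1 - rho²

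With k = 1 the ratio is (1 - rho²)/[2(1 - rho)] = (1 + rho)/2. For rho = 0.3, 0.5 and 0.7 it is 0.65, 0.75 and 0.85, that is 35%, 25% and 15% less variance. At rho = 0.5 the change-score test would need 40/0.75 = 53 per arm to match ANCOVA with 40.

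This depends on k. At rho = 0.5:

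| k | ANCOVA variance / change-score variance |
|---|---|
| 1 | 0.75 |
| 0.8 | 0.75/0.84 = 0.89 |
| 0.7 | 0.75/0.79 = 0.95 |
| 0.5 | 0.75/0.75 = 1.00 |

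With k above 1 the gain is larger than at k = 1.

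**The case against.** The strongest reply is that a t-test on change is a legitimate analysis of a randomised comparison, that the choice of covariates is usually left to the SAP, and that section 12.2 says a detailed SAP exists. Much of this stands. A reader might infer that the baseline is wasted or the estimate biased. Neither follows: a change score does use the baseline, with its coefficient fixed at 1, and it is unbiased under randomisation. Nor is the precision gain assured. Eligibility on PaO2/FiO2 or saturation may narrow the Day 1 spread, and step 4 shows that the gain can then vanish.

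A reader might also count nine primary tests and quote a false-positive chance of 20-25%. The documents do not support that. The six chi-square tests are an inference from two sections, section 12.2 only summarises the cut-offs, and the 20-25% needs a level of 0.05 per test, which the protocol never states. Its only level is 0.01.

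Finally, a reader might conclude that controls have no valid baseline. The definition by first dose does not describe them, but section 9.2 gives them a Day 1 sample, taken while they receive no study drug. This is loose wording with no demonstrated effect on the result.

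The reply does not remove the conflict. The protocol itself states two tests and two lists of measures, so a SAP that named one of each would have to override this text.

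**Conclusion.** The point holds as an internal conflict with no deciding rule: chi-square and t-test for the same endpoint, two measures or three, and neither a hierarchy nor a named primary test, against a sample size built on one difference in means at 0.01.

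The inflation at that level is modest: about 2-3% on the explicit t-tests, and about 4-7% on the widest reading, under assumed correlations of 0.6-0.9. The power cost would be substantial if chi-square decided (about 66-69% against 90%, with control response of 20-50% assumed), and nil if the t-test did. ANCOVA is a worthwhile improvement and not the correction of an invalid method. Its 15-35% saving in variance rests on assumed equal SDs and a correlation of 0.3-0.7. In large samples it is never less precise than the change score.

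**What to change.** In sections 4.1, 12.1 and 12.2, name one primary measure (for example PaO2/FiO2) and one deciding test: an ANCOVA of the Day 6 (or discharge) value on arm and Day 1 value, at the 0.01 level of section 12.1, with its sidedness stated. List the remaining measures and the 25/33/50% cut-offs as supportive, and use the same measures for the cut-offs in sections 4.1 and 12.2. Sections 3.1 and 5.1 restate the endpoint and need the same wording.

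As a minor wording change, define the control-arm baseline relative to randomisation, because a first dose does not exist for controls on Day 1.

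The cost is an amendment to the text and a matching SAP; no further patients or measurements are needed. The real price is that the sponsor gives up the other measures as primary claims.

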Data from the Wuhan COVID-19 epidemic show that patients that deteriorate are facing a prolonged period of mechanical ventilation. Therefore, from day 6 onwards, progressive patients in the active group will have the option to receive an additional 5 days of IV sargramostim, based on the treating physician's assessment. This group will be called group C. In the control group with progressive disease requiring non-invasive or invasive mechanical ventilatory support or developing ARDS, from day 6 onwards, the treating physician will have the option to initiate IV sargramostim 125mcg/m² body surface area once daily for 5 days. This group will be called group D. Comparisons of Group A (early 5 day intervention with sargramostim) with Group D (late 5 day intervention with sargramostim) will also be very informative.

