Comparisons between group A (early sargramostim) versus group B (no sargramostim) at day 6 will be important for reaching primary endpoint, and for key secondary endpoints. Comparisons of Group A (early 5 day intervention with sargramostim) with Group D (late 5 day intervention with sargramostim) will also be very informative for secondary endpoint analysis.

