9.4. Schematic overview of the data collection & interventions

10. Procedure	Screening	D1	D2-D5	D6/discharge	D7-D9	D10	Follow-up (10-20 weeks after D1)
Informed consent	X						
Inclusion/exclusion criteria	X						
Randomization		X					
Medical history & biometry	X						
Anamnesis and (S)AE inquiry	X						X
Concomitant medication	X						X
Physical examination ^l	X						X
6 Minutes Walk Test ^{o, i}							X
Vital signs ^a	X						X
ECG ^l				On clinical grounds			
Chest X-ray and/or (HR)CT scan				On clinical grounds			X ^m
Lung function ^l							X
Routine laboratory assessments^l on clinical grounds, except:	X	X ^b		X ^c			X ^c
- screening/day 1 and day 6/discharge							
Serum pregnancy test	X						
Study blood sampling							
- 5 ml serum tube		X		X			X
- 10 ml EDTA tube (selected centers only)							
Arterial blood gas^d		X		X			X
Score assessments							
- 6-point ordinal scale ^e							X
- Clinical sign score ^f							X
- NEWS2 score ^g							X
- SOFA score ^h		X		X		X	X
- HScore ⁱ		X		X			X
- CURB-65 ^j		X					

SARPAC

- APACHE II ^k		X					
- Glasgow Coma Scale	→						X
- HRCT fibrosis score ^m							X
IMP ⁿ		(X)	(X)	(X)	(X)	(X)	
Drug compliance		→					

^a Includes morning assessment (7-10 am) of T°C (actual and highest last 24h), Pulse rate, Blood Pressure, Respiratory Rate, SpO2 by pulseoximetry. Time point assessment (7-10 am) is not applicable for the Follow-Up visit.

^b Should minimally include haemoglobin, platelets, WBC count, eosinophils, lymphocytes, CD4 and CD8 T cell count, CRP, bilirubin, AST, ALT, LDH, creatinine, fibrinogen, triglycerides, ferritin, ureum, troponin, D-dimers.

^c Should minimally include haemoglobin, hematocrit, platelets, WBC count, neutrophils, eosinophils, lymphocytes, CD4 and CD8 T cell count, CRP, bilirubin, AST, ALT, LDH, creatinine, fibrinogen, triglyceride, ferritin, troponin, D-dimers, ESR, CK

^d Patient sitting upright breathing room air for a minimum of 3 minutes. If this is impossible due to dependency to supplemental oxygen, FiO2, oxygen flow rate, and method of oxygen delivery should be noted in the patient file. If arterial blood gas is taken within 24h before first dose administration, the arterial blood gas of screening can be used as D1 value.

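### The t-test of group A against group D compares early-treated patients with only those controls who progressed and were then given the drug, so it leans toward early sargramostim even if the drug does nothing

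*Protocol*

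**What the plan says.** Section 12.2 first describes the oxygenation analyses of group A against group B, with Day 6 as the primary time. It then adds: "The analyses described above will also be performed between group A (early 5 day intervention with sargramostim) and group D (late 5 day intervention". The outcomes named for the later time are "Change from baseline (D1) to Day 10, daily change from baseline (D1) at Day 10 in oxygenation/respiratory parameter", covering the P(A-a)O2 gradient, PaO2/FiO2 and SpO2/FiO2. The method is "A t-test will be conducted to compare the difference between the groups". No adjustment or caveat is attached.

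Group D is defined in section 5.1: "In the control group with progressive disease requiring non-invasive or invasive mechanical ventilatory support or developing ARDS, from day 6 onwards", the physician may start intravenous sargramostim. Section 7.1.1 gives the same rule without the ARDS route and expects 30% of patients to deteriorate.

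Section 7.1.1 describes group A in two ways. It is the patients treated for five days who do not worsen afterwards. It is also 40 patients, which is the whole active arm, from which about 12 may move on to group C.

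Sections 3.1 and 5.1 call the A-versus-D comparison very informative. Section 7.1.1 says that it "will also be very informative for secondary endpoint analysis".

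On timing, section 12.1 sets "Day 10 for patients who complete 10 days of treatment", while 12.2 says "Key timepoints of interest for endpoints include Day 6 and Day 11". In the section 9.4 schedule the row "Arterial blood gas" is marked at D1, D6/discharge and follow-up, and not at D10. The SOFA row is marked at D10, and its footnote lists PaO2 and FiO2 among the required inputs.

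**The concern.** Membership of D is decided after randomisation by the kind of event that the outcome measures. A control enters D by needing ventilatory support, or in 5.1 by developing ARDS, and by the physician then choosing to treat. Group A has no such entry condition and, on one wording, has the opposite one. The change from D1 in group D includes the very deterioration that put the patient there, before any late drug was given. A difference between A and D is therefore at least partly a difference in prognosis.

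The Day 6 version is weaker still. D patients may receive drug only from day 6, so at Day 6 the test sets treated patients against controls who had had no late treatment to speak of.

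The protocol presents the result as evidence on early versus late treatment. As planned, a p-value in favour of early treatment could come from selection alone and be reported as a secondary finding. The test is fixed in the protocol text, so this is not a detail left to the SAP.

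**Working it through.** **Inputs from the protocol.** 40 patients per arm (7.1.1, 12.1), 30% deteriorating (7.1.1), SD of 10 units (12.1), and a t-test (12.2).

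**The plan's own figure.** 0.30 × 40 = 12 deteriorating patients per arm, as 7.1.1 states. The sentence giving 12 for the control arm again names groups A and C; I read it as controls moving into D. Twelve is the most that D would hold under this rate, since entry also depends on the physician.

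**Assumption.** The protocol gives no correlation ρ between the oxygenation change and the tendency to progress. I show 0 to 0.9. A positive sign follows from the entry rule; the size does not.

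**Expected bias with no drug effect.** Let the oxygenation change be standard normal, and let a patient progress when a normal score with correlation ρ to it falls in the worst 30%.

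- Cut-point: z = −0.524, with normal density φ(z) = 0.3477.
- Mean of D: −ρ × 0.3477/0.30 = −1.159ρ.
- A as all 40 patients has mean 0, so A − D = 1.159ρ.
- A without its deteriorators has mean ρ × 0.3477/0.70 = 0.497ρ, so A − D = 1.656ρ.

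**False positives.** The next table comes from simulated trials with no drug effect (5,000 per setting) and a two-sample t-test at two-sided 0.05. It counts only significant results in favour of A, so the nominal rate is 2.5%. D averages 12 patients if every progressing control is treated, and 6 if half are.

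| ρ | A − D in SD, A all 40 | A − D in SD, A without deteriorators | All 40, D = 12 | Without deteriorators, D = 12 | All 40, D = 6 | Without deteriorators, D = 6 |
|---|---|---|---|---|---|---|
| 0 | 0 | 0 | 2.4% | 2.3% | 2.6% | 2.6% |
| 0.2 | 0.23 | 0.33 | 10% | 15% | 7% | 10% |
| 0.3 | 0.35 | 0.50 | 18% | 30% | 12% | 19% |
| 0.5 | 0.58 | 0.83 | 41% | 71% | 25% | 47% |
| 0.7 | 0.81 | 1.16 | 70% | 97% | 45% | 80% |
| 0.9 | 1.04 | 1.49 | 94% | 100% | 69% | 98% |

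If D is fixed at exactly 12 instead of averaging 12, the entry at ρ = 0.9 with all 40 in A is about 92%, and the other entries move little. With deterioration rates of 15% or 45% and ρ from 0.3 to 0.7, the bias is 0.27 to 1.28 SD. On the SD of 10 in 12.1, the main table spans about 2 to 15 units.

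**Day 10 data, passages side by side.**

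- 12.2 analyses the gradient and PaO2/FiO2 at Day 10. Both need an arterial gas.
- 9.4 marks no gas at D10, and 9.2 describes study gases only at D1 and at D6 or earlier discharge.
- The D10 SOFA in 9.4 needs PaO2, so the schedule is at odds with itself.
- 12.1 and most of 12.2 use Day 10, but one sentence of 12.2 uses Day 11.

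**The case against.** The strongest reply is that A versus D is secondary. Section 7.1.1 gives the primary and key secondary endpoints to A versus B at day 6, and A versus D carries no alpha or success rule of its own. That stands, and it limits the severity.

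Several stronger readings are tempting but not supported:

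- **That the test is near certain to favour early treatment whatever the truth.** The correlation is assumed. At 0.2 or 0.3 the false-positive rate is 10% or 18% with 12 in D, and lower with 6. Only the case of no drug effect was simulated.
- **That group A definitely excludes its deteriorators.** Section 7.1.1 supports both readings, so both are shown.
- **That only patients sick enough to have a clinical gas contribute at Day 10.** Section 12.1 uses discharge-day values for patients who leave earlier, a gas is scheduled at discharge before day 6, and the D10 SOFA implies a gas. What remains is that no D10 gas is marked, nor one at discharge on D7 to D9, so availability may be selective.
- **That the Day 10 value always precedes the last late dose.** The 9.4 footnote asks for drug after assessments only as far as practicable, and the start day of the late course is not fixed.

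It is also fair to say that comparing whole arms does not isolate early from late treatment, because most controls would never receive the drug.

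**Conclusion.** The point holds and should be fixed. It concerns a secondary analysis. The A-versus-D t-test is biased toward early sargramostim for any positive link between worse oxygenation and progression, and its Day 6 form cannot address late treatment.

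The direction rests on how group D is defined. The size rests on an assumed correlation (0.2 to 0.9), 30% deterioration, no drug effect and the number of controls who receive the drug. Whichever reading of group A is taken, the error rate exceeds the nominal one throughout that range. Even the mildest case shown (ρ = 0.2, all 40 in A, 6 in D) gives 7% against 2.5%.

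The unmarked D10 gas and the Day 10/Day 11 wording are smaller, separate inconsistencies. A reader might infer that the trial's main result is compromised. It is not: this test does not alter the randomised A-versus-B comparison at Day 6, although the meaning of group A should be made explicit there too.

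**What to change.** 1. In 12.2, remove the A-versus-D t-test and describe group D without a test. In 3.1, 5.1 and 7.1.1, remove the statement that the comparison informs early versus late treatment.
2. For Day 10 and later, compare all patients randomised to active (A + C) with all randomised to control (B + D), whatever drug was given after Day 6. Label this early versus deferred-optional treatment.
3. State that group A in the efficacy analyses means everyone randomised to active.
4. At Day 10, use SpO2/FiO2 where recorded and treat gas-based values as descriptive. Daily SpO2 in relation to FiO2 is promised in words only for the five-day treatment period. The NEWS2 change to day 10 (3.2, 4.2) needs SpO2, and 9.3 collects oxygen flow rate, so the value is likely but should be confirmed.
5. Reconcile Day 10 with Day 11, and the D10 blood-gas row with the D10 SOFA row, across 9.4, 12.1 and 12.2.

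**Cost.** Wording changes in 3.1, 5.1, 7.1.1, 9.4, 12.1 and 12.2, and no extra patients. The statistical price is a diluted contrast, since most controls never receive late drug. The trial would then give a valid answer on early versus deferred-optional treatment, and none on early versus late treatment in isolation.
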